6.5.1 Durvalumab and tremelimumab

For adverse events (AEs) that are considered at least partly due to administration of durvalumab (or durvalumab and tremelimumab for cycles 1-4) the following dose adjustment guidance may be applied:

- Treat each of the toxicities with maximum supportive care (including holding the agent suspected of causing the toxicity where required).
- If the symptoms promptly resolve with supportive care, consideration should be given to continuing the same dose of durvalumab or durvalumab and tremelimumab along with appropriate continuing supportive care. If medically appropriate, dose modifications are permitted for durvalumab and tremelimumab (see Appendix 1).
- All dose modifications should be documented with clear reasoning and documentation of the approach taken.

In addition, there are certain circumstances in which durvalumab or tremelimumab should be permanently discontinued.(see Section 4.3)

Following the first dose of durvalumab or tremelimumab, subsequent administration of durvalumab or tremelimumab can be modified based on toxicities observed (see Appendix 1).

Based on the mechanism of action of durvalumab or tremelimumab leading to T-cell activation and proliferation, there is the possibility of observing immune related Adverse Events (irAEs) during the conduct of this study. Potential irAEs include immune-mediated enterocolitis, dermatitis, hepatitis, and endocrinopathies. Subjects should be monitored for signs and symptoms of irAEs. In the absence of an alternate etiology (e.g., infection or PD) signs or symptoms of enterocolitis, dermatitis, hepatitis, and endocrinopathy should be considered to be immune-related.

Dose modification recommendations and toxicity management guidelines for immune-mediated reactions, for infusion-related reactions, and for non-immune-mediated reactions are detailed in Appendix 1.

In addition, management guidelines for adverse events of special interest (AESIs) are detailed in Section 10.1.3. All toxicities will be graded according to NCI CTCAE v4.03.

7. RESTRICTIONS DURING THE STUDY AND CONCOMITANT TREATMENT(S)

7. 1 Restrictions during the study

The following restrictions apply while the patient is receiving study treatment and for the specified times before and after:

Female patient of child-bearing potential

- Females of childbearing potential who are sexually active with a non-sterilized male partner must use at least 1 **highly** effective method of contraception (Table 1) from the time of screening and must agree to continue using such precautions for 180 days after the last dose of durvalumab + tremelimumab combination therapy or 90 days after the last dose of durvalumab monotherapy. Non-sterilized male partners of a female patient must use male condom plus spermicide throughout this period. Cessation of birth control after this point

should be discussed with a responsible physician. Not engaging in sexual activity for the total duration of the drug treatment and the drug washout period is an acceptable practice; however, periodic abstinence, the rhythm method, and the withdrawal method are not acceptable methods of birth control. Female patients should also refrain from breastfeeding throughout this period.

Male patients with a female partner of childbearing potential

- Non-sterilized males who are sexually active with a female partner of childbearing potential must use a male condom plus spermicide from screening through 180 days after receipt of the final dose of durvalumab + tremelimumab combination therapy or 90 days after receipt of the final dose of durvalumab monotherapy. Not engaging in sexual activity is an acceptable practice; however, occasional abstinence, the rhythm method, and the withdrawal method are not acceptable methods of contraception. Male patients should refrain from sperm donation throughout this period.
- Female partners (of childbearing potential) of male patients must also use a highly effective method of contraception throughout this period (Table).

Females of childbearing potential are defined as those who are not surgically sterile (ie, bilateral tubal ligation, bilateral oophorectomy, or complete hysterectomy) or post-menopausal.

Women will be considered post-menopausal if they have been amenorrheic for 12 months without an alternative medical cause. The following age-specific requirements apply:

- Women <50 years of age would be considered post-menopausal if they have been amenorrheic for 12 months or more following cessation of exogenous hormonal treatments and if they have luteinizing hormone and follicle-stimulating hormone levels in the post-menopausal range for the institution or underwent surgical sterilization (bilateral oophorectomy or hysterectomy).
- Women ≥ 50 years of age would be considered post-menopausal if they have been amenorrheic for 12 months or more following cessation of all exogenous hormonal treatments, had radiation-induced menopause with last menses >1 year ago, had chemotherapy-induced menopause with last menses >1 year ago, or underwent surgical sterilization (bilateral oophorectomy, bilateral salpingectomy or hysterectomy).

Highly effective methods of contraception, defined as one that results in a low failure rate (ie, less than 1% per year) when used consistently and correctly are described in Table 2. Note that some contraception methods are not considered highly effective (eg. male or female condom with or without spermicide; female cap, diaphragm, or sponge with or without spermicide; non-copper containing intrauterine device; progestogen-only oral hormonal contraceptive pills

where inhibition of ovulation is not the primary mode of action [excluding Cerazette/desogestrel which is considered highly effective]; and triphasic combined oral contraceptive pills).

Table 2. Highly effective methods of contraception (<1% failure rate)

Barrier/Intrauterine methods	Hormonal Methods

 • Copper T intrauterine device • Levonorgestrel-releasing intrauterine system (eg, Mirena®)^a 	
 • Etonogestrel implants: eg, Implanon or Norplan • Intravaginal device: eg, ethinylestradiol and etonogestrel • Medroxyprogesterone injection: eg, Depo-Provera • Normal and low dose combined oral contraceptive pill • Norelgestromin/ethinylestradiol transdermal system • Cerazette (desogestrel)

^a This is also considered a hormonal method

The following restrictions apply while the patient is receiving study treatment and for the specified times before and after:

Females of childbearing potential who are sexually active with a non-sterilized male partner must use 2 methods of effective contraception (Table 1) from the time of screening and must agree to continue using such precautions for 180 days after the last dose of durvalumab + tremelimumab combination therapy or 90 days after the last dose of durvalumab monotherapy, whichever is the longer time period; cessation of birth control after this point should be discussed with a responsible physician. Periodic abstinence, the rhythm method, and the withdrawal method are not acceptable methods of birth control.

–Females of childbearing potential are defined as those who are not surgically sterile (ie, bilateral tubal ligation, bilateral oophorectomy, or complete hysterectomy) or post-menopausal (defined 12 months with no menses without an alternative medical cause).

Non-sterilized males who are sexually active with a female partner of childbearing potential must use 2 acceptable methods of effective contraception (see Table 1) from screening through 180 days after receipt of the final dose of durvalumab + tremelimumab combination therapy or 90 days after receipt of the final dose of durvalumab monotherapy, whichever is the longer time period.

Restrictions relating to concomitant medications are described in Section 7.2.

Table 3. Effective methods of contraception (2 methods must be used)

Barrier methods	Intrauterine device methods	Hormonal methods
Male condom plus spermicide	Copper T	Implants
Cap plus spermicide	Progesterone T ^a	Hormonal shot or injection
Diaphragm plus spermicide	Levonorgestrel-releasing intrauterine system (eg, Mirena [®]) ^a	Combined pill Minipill Patch

^a This is also considered to be a hormonal method.

Blood donation

Subjects should not donate blood while participating in this study or for at least 90 days following the last infusion of durvalumab or tremelimumab.

7.2 Concomitant treatment(s)

The Principal Investigator must be informed as soon as possible about any medication taken from the time of screening until the end of the clinical phase of the study (final study visit). Restricted, prohibited, and permitted concomitant medications are described in the following sections. Refer to Appendix 1 for guidance on management of IP-related toxicities.

7.2.1 Permitted concomitant medications

Investigators may prescribe concomitant medications or treatments (e.g., acetaminophen, diphenhydramine) deemed necessary to provide adequate prophylactic or supportive care except for those medications identified as “excluded” as listed in Section 6.2.2.

7.2.2 Excluded Concomitant Medications

The following medications are considered exclusionary during the study.

1. Any investigational anticancer therapy other than the protocol specified therapies.
2. Any concurrent chemotherapy, radiotherapy (except palliative radiotherapy), immunotherapy, biologic or hormonal therapy for cancer treatment. Concurrent use of hormones for noncancer-related conditions (e.g., insulin for diabetes and hormone replacement therapy) is acceptable.

3. Immunosuppressive medications including, but not limited to systemic corticosteroids at doses not exceeding 10 mg/day of prednisone or equivalent, methotrexate, azathioprine, and TNF- α blockers. Use of immunosuppressive medications for the management of investigational product-related AEs or in subjects with contrast allergies is acceptable. In addition, use of inhaled and intranasal corticosteroids is permitted. A temporary period of steroids will be allowed for different indications, at the discretion of the principal investigator (e.g., chronic obstructive pulmonary disease, radiation, nausea, etc).
4. Live attenuated vaccines within 30 days of durvalumab and tremelimumab dosing (ie, 30 days prior to the first dose, during treatment with durvalumab and tremelimumab for 30 days post discontinuation of durvalumab and tremelimumab. Inactivated vaccines, such as the injectable influenza vaccine, are permitted.

Table 4. Prohibited and Rescue Medications

Prohibited medication/class of drug:	Usage:
Additional investigational anticancer therapy concurrent with those under investigation in this study	Should not be given whilst the patient is on IP treatment
mAbs against CTLA-4, PD-1, or PD-L1	Should not be given whilst the patient is on IP treatment through 90 days after the last dose of IP.
Any concurrent chemotherapy, local therapy (except palliative radiotherapy for non-target lesions, eg, radiotherapy, surgery, radiofrequency ablation), biologic therapy, or hormonal therapy for cancer treatment	Should not be given whilst the patient is on IP treatment. (Concurrent use of hormones for non-cancer-related conditions [eg, insulin for diabetes and hormone replacement therapy] is acceptable.)
Immunosuppressive medications, including, but not limited to, systemic corticosteroids at doses exceeding 10 mg/day of prednisone or its equivalent, methotrexate, azathioprine, and tumor necrosis factor α blockers	Should not be given whilst the patient is on IP treatment. (Use of immunosuppressive medications for the management of IP-related AEs or in patients with contrast allergies is acceptable. In addition, use of inhaled, topical, and intranasal corticosteroids is permitted.
Live attenuated vaccines	Should not be given through 30 days after the last dose of IP during the study

Prohibited medication/class of drug:	Usage:
VEGF inhibitors such as sunitinib, sorafenib and bevacizumab	Should not be given 90 days prior to first dose of investigational drug and with 30 days after last dose of investigational drug

Rescue/supportive medication/class of drug:	Usage:
Concomitant medications or treatments (eg, acetaminophen or diphenhydramine) deemed necessary by the Investigator to provide adequate prophylactic or supportive care, except for those medications identified as “prohibited” as listed above	To be administered as prescribed by the Investigator
Best supportive care (including antibiotics, nutritional support, growth factor support, correction of metabolic disorders, optimal symptom control, and pain management [including palliative radiotherapy, etc])	Should be used when necessary for all patients

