4.1 Inclusion criteria

1. Histologically proven recurrent/metastatic squamous cell carcinoma arising from a previous head and neck primary site, and located within the head and neck region, lung mediastinum, lymph nodes, soft tissue metastases or bone, and who are not candidates for curative intent therapy.
2. Be ≥ 18 years old at the time of signing informed consent and have an actual body weight $> 40\text{kg}$.
3. Demonstrated disease progression during, or after discontinuation, of the most recent line of systemic therapy.

4. Have received any number lines of prior systemic therapy (including systemic therapy in the curative intent setting, and including a platinum containing regimen).
5. Have received an anti-PD1 or anti PDL1 monoclonal antibody.
6. Have a target lesion/s deemed suitable by the treating physicians for hypofractionated radiation therapy (HIGRT or SBRT) with the intent of palliation or prevention of symptoms. This lesion must be: a) 1-3 non overlapping sites in the head and neck region OR b) metastatic lesions outside the H&N region in the lung mediastinum, soft tissue metastases, lymph nodes or bone (a minimum of 1 and a maximum 5 lesions will be irradiated), provided there is no significant overlap between the lesions. Patients should have RECIST 1.1 criteria measurable disease in addition to the lesion/s treated with radiation. If the site/s of radiation were previously radiated to high dose RT (>50Gy), there should be >6 month time interval between the last dose of radiation and the start of radiation. .
7. Have the ability to tolerate required radiotherapy-related procedures(eg: lie flat and hold position for treatment) as determined by the treating physician
8. Be willing and able to provide written informed consent for the trial and comply with the study visit requirements
9. Have measurable disease based on RECIST 1.1. (in addition to the lesion/s that will be treated with hypofractionated radiation therapy)
10. Have provided tissue from an archival tissue sample or newly obtained core or excisional biopsy of a tumor lesion.
11. Have a performance status of 0 or 1 on the ECOG Performance Scale.
12. Demonstrate adequate organ function as defined in below, based on screening labs should be performed within 10 days of treatment initiation.

- Hemoglobin ≥ 9.0 g/dL
- Absolute neutrophil count (ANC) $\geq 1.5 \times 10^9/L$ (≥ 1500 per mm 3)
- Platelet count $\geq 100 \times 10^9/L$ ($\geq 100,000$ per mm 3)

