4.2 Exclusion criteria

The subject ***must be excluded*** from participating in the trial if the subject:

1. Has a body weight ≤ 40 kg at the time of enrollment
2. Is currently participating in or has participated in a study of an investigational agent or using an investigational device within 4 weeks of the first dose of treatment.
3. Has a target lesion/s for radiotherapy that is > 5 cm (> 50 cc) in greatest dimension

4. Has a target lesion/s in a region that previously received high dose RT (>50 Gy) demonstrating any of the following:
 - a. carotid artery encasement (> 180 degrees)
 - b. unprotected carotid artery (i.e. skin is directly over the carotid without intervening soft tissue, especially after prior neck dissection without a vascularized free flap) (a&b due to risk of carotid blow out)
 - c. skin infiltration by tumor (due to risk of fistula)
 - d. located in the larynx/hypopharynx primaries (due airway threat) treated with high dose radiation therapy (>50 Gy) within 6 months or less of trial enrollment
5. Any prior Grade ≥ 3 immune-related adverse event (irAE) while receiving a prior immunotherapy agent, or any unresolved irAE >Grade 1
6. Current or prior use of immunosuppressive medication within 14 days before the first dose of durvalumab or tremelimumab. The following are exceptions to this criterion:
 - Intranasal, inhaled, topical steroids, or local steroid injections (eg, intra articular injection)
 - Systemic corticosteroids at physiologic doses not to exceed 10 mg/day of prednisone or its equivalent
 - Steroids as premedication for hypersensitivity reactions (eg, CT scan premedication)
7. Has received a prior monoclonal antibody within 4 weeks prior to study Day 1 or who has not recovered (i.e., \leq Grade 1 or at baseline) from adverse events due to agents administered more than 4 weeks earlier.
8. Has received prior chemotherapy, targeted small molecule therapy, or radiation therapy within 2 weeks prior to study Day 1 or who has not recovered (i.e., \leq Grade 1 or at baseline) from adverse events due to a previously administered agent.
-Note: Subjects with \leq Grade 2 neuropathy are an exception to this criterion and may qualify for the study.

-Note: If subject received major surgery, they must have recovered adequately from the toxicity and/or complications from the intervention prior to starting therapy.

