5.2.2 Duration of treatment and criteria for retreatment

For patients receiving durvalumab + tremelimumab, retreatment is allowed (once only) for patients meeting the retreatment criteria below. The same treatment guidelines followed during the initial 12-month treatment period will be followed during the retreatment period, including the same dose and frequency of treatments and the same schedule of assessments. Radiotherapy is not required during retreatment, although it may be considered per the discretion of the treating physician.

Patients receiving the combination of durvalumab and tremelimumab may undergo retreatment in 2 clinical scenarios, described below:

1. Patients who achieve and maintain disease control (ie, CR, PR, or SD) through to the end of the 12-month treatment period may restart treatment with the combination upon evidence of PD, with or without confirmation according to RECIST 1.1, during follow-up.
2. Patients who complete the 4 dosing cycles of the combination of durvalumab and tremelimumab portion of the regimen (with clinical benefit per Investigator judgment), but subsequently have evidence of PD during the durvalumab monotherapy portion of the combination regimen, with or without confirmation according to RECIST 1.1, may restart treatment with the combination.
3. For the durvalumab + tremelimumab treatment group, before restarting their assigned treatment, the Investigator should ensure that the patient:

- a. Does not have any significant, unacceptable, or irreversible toxicities that indicate continuing treatment will not further benefit the patient
- b. Still fulfils the eligibility criteria for this study, including re-consenting to restart durvalumab and tremelimumab
- c. Has not have received an intervening systemic anticancer therapy after their assigned treatment discontinuation.
- d. Has had a baseline tumor assessment within 28 days of restarting their assigned treatment; all further scans should occur with the same frequency as during the initial 12 months of treatment (relative to the date of randomization) until study treatment is stopped (maximum of 13 cycles).

During the retreatment period, patients (> 30kg) receiving durvalumab + tremelimumab may resume durvalumab dosing at 1500 mg q4w with 75 mg of tremelimumab q4w for 4 doses each. Patients will then continue with durvalumab monotherapy at 1500 mg q4w, beginning at Week 16, for a total of 13 doses.

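### Section 7.2.2 sets conflicting limits on non-protocol palliative radiotherapy, so a RECIST-measured lesion could be irradiated and its shrinkage counted in the secondary response rate

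*Combined protocol and SAP*

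**What the plan says.** Three provisions of Section 7.2.2 bear on palliative radiotherapy that is not part of the protocol course.

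- **Item 2** of the exclusion list gives its radiotherapy entry as "radiotherapy (except palliative radiotherapy". No lesion is specified.
- **Table 4, prohibited row** bars local therapy while the patient is on study drug, "except palliative radiotherapy for non-target lesions".
- **Table 4, best-supportive-care row** includes "pain management [including palliative radiotherapy, etc", and its usage column says "Should be used when necessary for all patients". The row directly above excepts anything listed as prohibited; this row does not.

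In the eligibility criteria, target lesion means the site chosen for protocol radiotherapy. Section 4.1 item 6 reads "Have a target lesion/s deemed suitable by the treating physicians for hypofractionated radiation therapy", and Section 4.2 item 3 reads "Has a target lesion/s for radiotherapy". Section 4.1 item 9 separately requires disease that can be measured outside that field: "Have measurable disease based on RECIST 1.1. (in addition to the lesion/s that will be treated with hypofractionated radiation therapy".

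Section 9 derives the efficacy endpoints by program from RECIST 1.1, and Section 11.2.2 refers to the same criteria. Neither these sections nor 9.1 adds a rule for a measured lesion irradiated outside the protocol. Section 11.3 sets no response threshold: objective responses among the 20 patients would be grounds for a larger study.

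**The concern.** Inclusion item 9 allows response to be read in lesions that the protocol radiation does not treat. If one of those lesions is later irradiated for symptoms, its shrinkage may be a local effect of the extra radiotherapy rather than of the study combination.

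The situation is plausible. Patients enter because a lesion needs palliation, and Section 9 lets study drug continue while progression awaits confirmation, so symptomatic lesions outside the protocol field can arise on treatment. With 20 patients and no threshold, a single response of this kind could turn a result with no responses into one with a response.

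**Working it through.** **Step 1. The three provisions side by side.** Does each allow non-protocol palliative radiotherapy to a RECIST target lesion outside the protocol field, during treatment?

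| Provision | Lesion limit | Target lesion in the RECIST sense | Target lesion in the eligibility sense (radiotherapy site) |
|---|---|---|---|
| Item 2 | none | allowed | allowed |
| Prohibited row | non-target only | barred | allowed |
| Best-supportive-care row | none | allowed | allowed |

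Only the prohibited row protects the measured lesions, and only if its term is read in the RECIST sense.

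**Step 2. Does other text settle it?** Section 7.2.1 permits supportive treatments except excluded ones, but points to a Section 6.2.2 that does not exist; 6.2 covers dosage and administration. If 7.2.2 was meant, item 2 and its unrestricted exemption are part of that very list. No text ranks the provisions.

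**Step 3. Size.** Input: n = 20 (Section 11.3). The plan's own figures confirm this basis:

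- Half-width: 1.96 × √(0.25/20) = 21.9%, against the stated 22%.
- Chance of seeing an event with 10% prevalence: 1 − 0.9^20 = 87.8%, against the stated minimum of 87%.

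Effect of one converted non-responder on ORR: 1/20 = 5 points. Exact (Clopper-Pearson) 95% intervals:

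- 0/20: upper limit 1 − 0.025^(1/20) = 16.8%, so 0 to 16.8%.
- 1/20: 0.1 to 24.9%.

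The effect is zero for a patient who had already responded, had already progressed, or still falls short of response.

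**Step 4. Frequency (assumed, for scale only).** Let f be the probability that a patient is converted to a counted response by such radiotherapy, with patients independent. Expected ORR inflation is f. The chance of at least one such response is 1 − (1 − f)^20:

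| f | Chance of at least one in 20 |
|---|---|
| 0.5% | 10% |
| 1% | 18% |
| 2% | 33% |
| 5% | 64% |

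Not every irradiated patient converts, so f cannot exceed the share of patients irradiated and would generally be smaller.

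**The case against.** The strongest reply is that the ban already exists. The prohibited row is the most specific provision, and in a concomitant-therapy table non-target lesion is naturally the RECIST term. The radiation sections mostly call the irradiated site the index lesion, which weakens the competing meaning. Reading the specific row as limiting the general ones would reconcile the text, and 7.2.1 shows a general intent that supportive care should not override exclusions.

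Most of this stands as the likely intent, but it does not remove the conflict. Item 2 sits in the exclusion list itself and carries no lesion limit. The supportive-care row positively calls for the treatment when needed. The eligibility criteria give the key term another meaning.

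Other parts of the reply also stand:

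- What RECIST 1.1 does with a locally treated lesion cannot be checked from these documents. The plan is silent only in the sense that it adds no rule of its own.
- The case report forms are not shown. Section 7.2 asks about medication, and 6.1.1 reviews new anti-cancer therapy after the last dose, but Section 14 has source records transcribed to the forms. Radiotherapy dates and sites may well be captured.
- ORR is secondary and descriptive, and Section 1.2 describes the response data as hypothesis-generating.
- Refusing every later response would drop genuine responses in unirradiated lesions, which matter to the abscopal rationale. The fix should leave room to report them.

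**Conclusion.** The inconsistency is real and worth correcting, but minor. Two of three provisions in Section 7.2.2 allow palliative radiotherapy to a measured lesion, the third probably forbids it, and nothing says which governs. The possible effect is 5 ORR points per converted patient at n = 20.

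Four stronger inferences are not supported:

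- A reader might infer that the protocol plainly permits irradiating measured lesions. It does not; the prohibited row probably bars this on treatment.
- A reader might infer that such shrinkage would certainly be counted. That depends on how RECIST 1.1 is applied, which cannot be verified here.
- A reader might infer that the radiotherapy would go unrecorded. The forms are not available to show this.
- A reader might take the 10% to 64% range as an estimate. It follows only from chosen values of f.

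The primary safety endpoint is not affected by this point. Progression-free survival could shift toward later progression, by an amount that cannot be estimated.

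**What to change.** Use one limit in item 2, the prohibited row and the best-supportive-care row: *palliative radiotherapy to lesions that are not RECIST target lesions*, with the protocol radiation course explicitly exempt.

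If a RECIST target lesion must be irradiated for symptoms, give the radiotherapy and record its date and site. Then state in 11.2.2 that:

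- a response first reached after that date is not counted in the main ORR;
- earlier responses stand;
- the patient stays in the denominator, consistent with 11.1, which includes all enrolled patients;
- any later response in unirradiated lesions may be reported descriptively.

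Two additions are optional. One is a progression-free survival sensitivity analysis that counts such radiotherapy as an event. The other is a reference to the same limit in 5.2.2, which now says "Radiotherapy is not required during retreatment, although it may be considered per the discretion of the treating physician"; retreatment follows progression, so first-course progression-free survival would not change.

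The cost is wording in 7.2.2 (including Table 4) and 11.2.2, and a date and site field if the forms lack one. A few later genuine responses would be left out of the main ORR. Palliation is not withheld, and the sample size and primary endpoint stay as they are.

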9. Has a known additional malignancy that is progressing or requires active treatment. Exceptions include basal cell carcinoma of the skin, squamous cell carcinoma of the skin, or in situ cervical cancer that has undergone potentially curative therapy.
10. Has known brain metastases or spinal cord compression unless the patient is stable (asymptomatic; no evidence of new or emerging brain metastases; and stable and off steroids for at least 14 days prior to start of study treatment). Following radiotherapy and/or surgery of the brain metastases patients must wait 4 weeks following the intervention and before initiating study treatment with imaging to confirm stability.
11. Has an active autoimmune disease requiring systemic treatment within the past 2 years or a documented history of clinically severe autoimmune disease, or a syndrome that requires systemic steroids or immunosuppressive agents. Subjects with vitiligo or resolved childhood asthma/atopy would be an exception to this rule. Subjects that require intermittent use of bronchodilators or local steroid injections would not be excluded from the study. Subjects with hypothyroidism stable on hormone replacement will not be excluded from the study.
12. Has evidence of current interstitial lung disease (ILD) or pneumonitis or a prior history of ILD or pneumonitis requiring oral or intravenous glucocorticoids
13. Has an active infection requiring systemic therapy.
14. Requires therapeutic anticoagulation or has known active bleeding diathesis
15. Has a history or current evidence of any condition, therapy, or laboratory abnormality that might confound the results of the trial, interfere with the subject's participation for the full duration of the trial, or is not in the best interest of the subject to participate, in the opinion of the treating investigator.
16. Has known psychiatric or substance abuse disorders that would interfere with cooperation with the requirements of the trial.

17. Is pregnant or breastfeeding, or expecting to conceive or father children within the projected duration of the trial, starting with the pre-screening or screening visit through 180 days after the last dose of trial treatment.
18. Has received prior therapy with an anti-Cytotoxic T-lymphocyte-associated antigen-4 (CTLA-4) antibody (including ipilimumab or any other antibody or drug specifically targeting T-cell co-stimulation or checkpoint pathways).

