11.0 STATISTICAL METHODS AND SAMPLE SIZE DETERMINATION

11.1 Description of analysis sets

All patients enrolled in the study, including those who were replaced in the run-in phase (see Section 4.4) will be included in the analysis of toxicity and efficacy.

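### Section 7.2.2 item 3 states the on-study steroid limit backwards: it excludes prednisone-equivalent doses of 10 mg/day or less, while Table 4 prohibits doses above 10 mg/day

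*Combined protocol and SAP*

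**What the plan says.** Two places set a general limit on systemic corticosteroids during the study, and both are in Section 7.2.2.

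- Item 3 of the numbered list, under an opening sentence that makes everything listed exclusionary, covers immunosuppressive drugs in general and names "systemic corticosteroids at doses not exceeding 10 mg/day of prednisone or equivalent".
- The matching row of Table 4 names "systemic corticosteroids at doses exceeding 10 mg/day of prednisone or its equivalent" as not to be given while the patient is on investigational product.

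Both entries give the same other examples (methotrexate, azathioprine, TNF-alpha blockers) and the same exceptions for product-related adverse events and contrast allergy. Item 3 alone adds: "A temporary period of steroids will be allowed for different indications, at the discretion of the principal investigator".

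Exclusion criterion 6 (Section 4.2, repeated in the Synopsis) lists as an exception to its bar on recent immunosuppressants: "Systemic corticosteroids at physiologic doses not to exceed 10 mg/day of prednisone or its equivalent". Section 7.2.1 allows investigators to prescribe drugs "deemed necessary to provide adequate prophylactic or supportive care except for those medications identified as" excluded.

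**The concern.** A prohibited-medication rule should give one answer for a given drug and dose. Here, a patient on a continuous low systemic dose who entered properly under exclusion 6 would be in breach of item 3 from the first day of treatment, yet compliant with Table 4. Two monitors could classify the same patient differently and each cite Section 7.2.2. An investigator following item 3 could also stop a drug that the rest of the protocol accepts.

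In the other direction, item 3 does not expressly name the higher doses, which are the ones that matter for immunosuppression in a checkpoint-inhibitor trial.

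What is at stake is consistent prescribing and consistent deviation calls. It is not the statistical design.

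**Working it through.** No figure in the plan needs reproducing, and no sample-size or power calculation applies. The check sets the texts side by side.

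**Inputs**

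| Text | Role | Range named (prednisone equivalent) |
|---|---|---|
| 7.2.2 item 3 | excluded on study | 10 mg/day or less |
| 7.2.2 Table 4 | prohibited on study | above 10 mg/day |
| 4.2 and Synopsis, exclusion 6 | allowed at entry | 10 mg/day or less |
| Appendix 1, general guidance and endocrinopathy | compatible with further study drug | 10 mg/day or less |

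The first two rows are the only general on-study limits. They share no dose, and together they cover every dose. Exclusion 6 is an entry criterion, and the Appendix 1 statements concern steroid taper and re-dosing after immune-related events. Neither is a general on-study limit, but both show the intended direction, and it is Table 4's.

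**Three illustrative doses, outside every exception**

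| Dose | Item 3 as written | Table 4 | Item 3 without *not* |
|---|---|---|---|
| 5 mg/day | excluded | not prohibited | not named |
| 10 mg/day | excluded | not prohibited | not named |
| 15 mg/day | not named | prohibited | named |

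The doses are chosen only to show the direction of each limit. At 5 and 10 mg/day the two texts give opposite answers. At 15 mg/day item 3's named limit is silent, although its open-ended wording could still catch the drug as an immunosuppressive. With *not* removed, the named limits agree at all three doses.

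**Who is affected**

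Start from continuous systemic steroid use at 10 mg/day or less and remove what other text already handles:

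1. Exclusion 11 keeps out anyone with "a syndrome that requires systemic steroids or immunosuppressive agents".
2. Physiologic replacement arguably falls under the allowance in item 2 and Table 4: "Concurrent use of hormones for noncancer-related conditions".
3. Item 3 itself excepts product-related adverse events, contrast allergy and temporary courses at the principal investigator's discretion.

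What remains is continuous use at 10 mg/day or less outside all of these. The documents give no rate of steroid use, so the size of this group cannot be estimated.

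**Effect on the analysis**

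Section 11.1 states that all enrolled patients, including those replaced in the run-in, "will be included in the analysis of toxicity and efficacy". A steroid deviation therefore removes nobody from an analysis set. The sample-size reasoning in Section 11.3, the DLT definition in Section 6.4 and the stopping rule in Section 3.3 do not use the steroid limit in item 3.

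**The case against.** The strongest reply is that no careful reader would be misled. A rule that bars 5 mg/day of prednisone and names no limit on high doses makes no sense in a list of immunosuppressives. The correct wording follows in Table 4, and exclusion 6 and Appendix 1 confirm it. This stands as evidence of intent and is why the point is minor. It does not remove the contradiction, because site staff and monitors should not have to decide which of two limits in one section to follow.

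A second reply is that item 3 is not limited to its named examples, so 15 mg/day could still be excluded under the general term. This also stands. The firm conflict is at 10 mg/day and below, where the open-ended wording makes no difference.

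Third, the exceptions cover most realistic use, and the temporary-steroid sentence has no dose or duration limit. This is correct, and it is why no number of patients is claimed.

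Fourth, Section 7.2.1 points to a Section 6.2.2 that does not exist, so its link to this list is an inference. The inference is reasonable, since Section 7.2.2 is the list of excluded drugs. Item 3 is in any case operative through its own section's opening sentence.

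**Conclusion.** The concern holds, at minor severity. Section 7.2.2 contains two general steroid limits that run in opposite directions, and item 3 is the wrong one. For continuous systemic doses of 10 mg/day or less outside the exceptions, item 3 excludes what Table 4 does not prohibit. Above 10 mg/day, item 3 does not expressly name what Table 4 prohibits.

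The conclusion about direction rests on reading exclusion 6 and Appendix 1 as showing intent. The conflict itself rests only on the wording of the two entries. Nothing in the sample size, safety rules or analysis changes.

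**What to change.** Delete the word *not* from the steroid clause in Section 7.2.2 item 3, so that it excludes doses above 10 mg/day of prednisone or equivalent, as Table 4 does. Leave exclusions 6 and 11 and Appendix 1 as they are.

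Separately, the sponsor should decide whether the temporary-steroid allowance, now only in item 3, also applies to the Table 4 prohibition. The text does not settle this, and deleting *not* will not settle it either.

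The cost of the main change is one word, with no effect on design, sample size or analysis.
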